2. Compare the effectiveness of the two intervention sequences (1st cognitive training and 2nd mindfulness versus 1st mindfulness and 2nd cognitive training) on neurocognitive, biopsychological, biomarker, and connectome outcome variables.

METHODS

1. Study Design 3: In this single-center study (La Paz University Hospital), the pilot phase of a randomized, counterbalanced, crossover controlled clinical trial with a recycled waiting list will be conducted according to CONSORT standards. (Boutron et al., 2017).

2. Participants: A total of 40 patients (20 patients initially in the clinical trial phase and 20 on the waiting list) between the ages of 8 and 18 will be recruited from the three clinical groups in Study 1, requiring compliance with inclusion criteria (having a computer, mobile phone, or tablet with an Internet connection) and exclusion criteria (CI < 80 in Matrices). These 40 patients will be recruited from the sample participating in Study 1 using a strategic/intentional non-random sampling technique.

3. Outcome variables: In pre-/post-intervention phases, primary variables will be measured using performance tests: processing speed (SDMT); sustained visual attention (CPT-3); working memory, implicit, immediate/delayed auditory-verbal, visual-spatial, and intermodal [Clinical Memory Assessment (ECM)]; verbal fluency [Verbal Fluency Test (VFT)]; resistance to visual interference [Colors and Words Test (STROOP)]. Secondary variables in pre-/post-intervention phases are questionnaires measuring: executive functions [BRIEF-2, parent-completed version]; pain intensity and interference [BPI, self-reported by patient]; sleep quality [PROMIS and AIQ, self-reported by patient]; emotional and behavioral problems [BASC-3, parent and self-reported versions]; and mindfulness, trait level [Children and Adolescent Mindfulness Measure (CAMM)]; as well as biomarkers (inflammatory and immunological) and a neurofunctional analysis (connectome), using electroencephalogram (EEG) recordings. In the intermediate phase (3 months after the start of treatment), the BASC-3 questionnaire will be administered. Finally, at the 6-month follow-up after the end of both interventions, the BRIEF-2, BASC-3, BPI, AIQ, and PROMIS questionnaires will be included.

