
5. Statistical analyses: The statistical analyses for this third study will be described jointly for the two established objectives.

First, mixed 2x3 ANCOVAs will be used (intergroup factor, with two levels: experimental group versus control; and repeated measures factor, with three levels: pre-intervention, post-intervention, and six months), controlling for confounding variables (time elapsed since completion of the last treatment received: chemotherapy, TPH, or CAR-T). However, in the event of non-compliance with statistical assumptions such as normality, non-parametric analog models will be used. In turn, latent growth curve models will be developed.

As for the intergroup factor, Tukey's HSD parametric tests (for homoscedastic contrasts) and Games-Howell tests (for heteroscedastic contrasts) will be used to control the type I error rate per family of comparisons. Likewise, in the event of non-compliance with parametric assumptions such as normality, the Mann-Whitney U test will be used for pairwise comparisons, controlling the type I error rate with the Bonferroni correction. Regarding the intragroup factor, parametric pairwise contrasts will be performed using Tukey's WSD test (for spherical contrasts) and the

Roy-Bose test (for non-spherical contrasts); and non-parametric pairwise comparisons will be performed using the Wilcoxon test together with a Dunn-Sidak post hoc correction.

In turn, these parametric hypothesis testing procedures will be complemented with effect size indices such as omega squared, as an omnibus index, and Cohen's d, as an index for pairwise comparisons.

Conversely, where appropriate, for the intergroup factor, effect size indices for nonparametric tests such as Freeman's Theta, as an omnibus index, and Cliff's Delta, as an index for pairwise comparisons, will be used. On the other hand, for the intragroup factor, Kendall's W-type omnibus effect size indices will be applied, as well as the biserial correlation for dependent pair ranks in order to perform multiple comparisons.

Finally, for the interactive term, the effect size index f will be chosen as an omnibus test, and Cohen's d indices for simple effects.

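### For the three time contrasts, Roy-Bose is dominated by Holm-adjusted paired contrasts; the loss is modest and confined to secondary questionnaires

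*Protocol*

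**What the plan says.** METHODS, 5. Statistical analyses specifies a 2x3 mixed ANCOVA with a "repeated measures factor, with three levels: pre-intervention, post-intervention, and six months". Parametric pairwise contrasts on that factor follow one of two routes: Tukey's "WSD test (for spherical contrasts"), or the "Roy-Bose test (for non-spherical contrasts"). For the non-parametric route, "non-parametric pairwise comparisons will be performed using the Wilcoxon test together with a Dunn-Sidak post hoc correction". Family-wise control is stated for the intergroup factor ("to control the type I error rate per family of comparisons"); I take it to be meant for the time factor too.

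METHODS, 2. Participants gives the size: "A total of 40 patients (20 patients initially in the clinical trial phase and 20 on the waiting list"). METHODS, 3. Outcome variables limits the primary outcomes to two occasions: "In pre-/post-intervention phases, primary variables will be measured using performance tests". Only the BRIEF-2, BASC-3, BPI, AIQ and PROMIS questionnaires are repeated at six months. The BASC-3 also has an intermediate administration at three months, which is not a level of the ANCOVA.

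**The concern.** Roy-Bose is built for simultaneous statements about all contrasts among the repeated means, and its critical value rises to pay for that. The Protocol announces only pairwise contrasts for this factor, and with three levels there are three. The extra protection is paid for and not used.

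The non-spherical route may well be the one taken. PROJECT DEVELOPMENT STAGES puts the experimental group's assessments in November-December 2025, July-August 2026 and December 2026, that is, gaps of about 8 and then 4 to 5 months. If correlations fall with elapsed time, the three differences have unequal variances.

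At stake is the power of within-group statements on gain and its maintenance for the questionnaires, in a trial of 40 patients.

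**Working it through.** The Protocol states no alpha, power, effect size or SD, so there is no figure of its own to reproduce. Assumptions: two-sided family-wise alpha 0.05; Tukey's WSD, which the Protocol does not define, read as a studentized-range test with pooled within-subject error; sphericity judged by Mauchly's test at 5%.

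**Inputs.** k = 3 time levels give k(k-1)/2 = 3 pairs. Error df are v = 20 - 1 = 19 within one group, or v = 40 - 2 = 38 with two groups pooled, before losing 1 df to the covariate.

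**Formulas for the critical |t|.**
- Roy-Bose: sqrt[ v(k-1)/(v-k+2) x F(0.95; k-1, v-k+2) ]
- Holm: t(1 - 0.05/6; v), t(1 - 0.05/4; v), t(1 - 0.05/2; v)
- WSD: q(0.95; k, v(k-1))/sqrt(2), used with a pooled error

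For Roy-Bose at v = 19: sqrt[(38/18) x F(0.95; 2, 18)] = sqrt(2.111 x 3.555) = 2.739. At v = 38: sqrt[(76/37) x F(0.95; 2, 37)] = sqrt(2.054 x 3.252) = 2.584.

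| v | Roy-Bose | Holm steps 1 / 2 / 3 | WSD |
|---|---|---|---|
| 19 | 2.739 | 2.625 / 2.433 / 2.093 | 2.439 |
| 38 | 2.584 | 2.505 / 2.334 / 2.024 | 2.390 |

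**Roy-Bose against Holm.** Both use the paired t with the variance of that pair. Any |t| above the Roy-Bose value also exceeds Holm's largest step, so it is rejected whatever its rank. This needs no assumption about effects or correlations.

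**Size of the gain.** Simulation, 20,000 data sets per setting, one group of 20. Correlations are listed as pre-post, post-6m, pre-6m; means are in SD units. Average power is over the true contrasts.

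| Correlations | Means | Roy-Bose | Holm | Gain (points) |
|---|---|---|---|---|
| 0.8, 0.5, 0.4 | 0 / 0.5 / 0.25 | 30.4% | 33.9% | 3.5 |
| 0.7, 0.7, 0.5 | 0 / 0.5 / 0.25 | 25.4% | 30.3% | 4.9 |
| 0.8, 0.5, 0.4 | 0 / 0.5 / 0.5 | 52.5% | 59.1% | 6.6 |
| 0.7, 0.7, 0.5 | 0 / 0.8 / 0.4 | 50.6% | 59.6% | 9.0 |

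In the third row, power for at least one true contrast goes from 79.9% to 83.1% (3.2 points), and for both from 25.1% to 35.1% (10.0 points). Under the null with the same correlations, family-wise error is 3.4% for Roy-Bose and 4.2% for Holm.

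**Holm against the whole two-branch rule.** Here the direction varies. With two groups of 20 pooled, means 0/0.35/0.15 and correlations 0.65, 0.80, 0.50, the planned rule detects pre-post in 55% and post-6m in 29%; Holm detects 59% and 36%. In one group of 20:
- same means and correlations: pre-post 26.1% planned against 26.1% Holm; post-6m 11.2% against 15.8%; pre-6m 6.7% against 5.4%
- equal correlations of 0.6, same means: pre-post 25.8% planned against 22.8% Holm
- correlations 0.70, 0.80, 0.60, means 0/0.3/0.3: at least one contrast 32.9% planned against 28.3% Holm

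**Primary performance tests.** With k = 2 there is one contrast, and all three critical values coincide (2.093 at v = 19; 2.024 at v = 38). Nothing changes.

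**The case against.** The strongest reply is that the Protocol names recognised procedures and provides a branch for non-sphericity, so choosing among valid adjustments is a matter of taste. The first part stands: nothing here is contradictory, and Roy-Bose holds its error rate. The second part does not fully stand, because a method that never rejects more than its alternative, at the same nominal error rate and for the same three contrasts, is not an equal choice.

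A reader might infer that Holm gives more power than the whole planned rule, Tukey's WSD included. The calculations do not support this. WSD's critical value lies below Holm's first step at both df, and in one group of 20 Holm loses in some settings. One group is also the relevant case for maintenance, because waiting-list patients start treatment after 24 weeks and have no untreated six-month value. Part of WSD's advantage under non-sphericity is not genuine, since its pooled error is too small for the pre-6m pair: with correlations 0.8, 0.5, 0.4 and n = 20, WSD used without the check has a family-wise error of 6.1%. Under true sphericity its advantage on the first contrast is real.

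A reader might also infer that the non-parametric branch should move from Dunn-Sidak to Holm for the same reason. That is not a uniform improvement: the Sidak threshold for three tests is 1 - 0.95^(1/3) = 0.01695, while Holm's first is 0.05/3 = 0.01667.

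Finally, both stated hypotheses are between-group comparisons, which pairwise time contrasts do not test. That stands and limits the importance of the point.

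**Conclusion.** The point holds against Roy-Bose only. For three planned pairwise contrasts Roy-Bose is dominated by Holm-adjusted paired contrasts; this is arithmetic and rests on no assumed effect. The size of the gain does rest on assumptions (alpha 0.05, effects, correlations), since the Protocol gives none. It is about 3 to 5 points per contrast in one group of 20 at modest effects and up to about 8 with two groups pooled; larger assumed effects give somewhat more, as the last two table rows show.

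The gain is confined to the secondary questionnaires with a six-month value (BRIEF-2, BASC-3, BPI, PROMIS, AIQ). It does not touch the primary performance tests or the between-group hypotheses. It would be wrong to conclude that the planned tests are invalid: at n = 20 the two-branch rule had a simulated family-wise error of 4.9% to 5.4%. This is an inexpensive improvement, not a defect that threatens the trial.

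**What to change.** In METHODS, 5. Statistical analyses, replace the Roy-Bose test by paired contrasts, each with its own variance, Holm-adjusted over the planned pairs. The cost is one sentence and no extra data. Simultaneous intervals for arbitrary contrasts are lost, but none is planned.

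Optionally, use the same Holm contrasts in place of Tukey's WSD. This removes the sphericity check for these contrasts and WSD's liberal error for the pre-6m pair, at some cost in power for the first contrast when sphericity truly holds. It does not remove sphericity from the omnibus ANCOVA tests.

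If WSD is kept, its leak when the check misses non-sphericity remains. With correlations 0.8, 0.5, 0.4 and n = 20, the planned rule's null error is 4.9%. Swapping only Roy-Bose for Holm can add at most 4.2% - 3.4% = 0.8 points, hence at most 5.7%. The sponsor should choose between the two versions knowingly. The Dunn-Sidak correction for the Wilcoxon comparisons can stay.

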Finally, multiple regression analyses will be performed to predict post-treatment and 6-month follow-up measures (neurocognitive and biopsychological), coding some measures from Study 1 as predictors, such as: processing speed levels, sustained visual attention, verbal fluency, and resistance to visual interference.

6. Limitations, biases, and contingency plan: given that participant loss is expected in any clinical trial, additional participants from the previous study will be recruited in such a scenario. The multi-method evaluation approach used (objective neurocognitive tests, questionnaires, biomarkers, and connectome) will avoid the common method bias (Podsakoff et al., 2012). Anticipating the temporary limitation on pre-/post-intervention assessment tasks as a potential risk to implementation, the age-differentiated treatment editions will be implemented partially simultaneously, with a one-month delay in the start of the intervention for each age group, using that month for the pre-intervention assessment of the other group.

This project will be carried out in accordance with the ethical principles of the Fortaleza Declaration of Helsinki (2013), strictly respecting confidentiality and the requirements of Spanish/European data protection regulations, as well as the provisions of the biomedical research law (Law 14/2007, of July 3); the informed consent of patients and their legal guardians will be required.

Finally, given that the objectives of these studies have not been scientifically addressed to date in the child and adolescent population receiving CAR-T therapies, this project will make a novel, original, and relevant contribution at the scientific-clinical level, and is in line with one of the strategic lines of our institution, IdiPAZ, and its core hospital, given that it coordinates the **European Reference Network TransplantChild**.

DATA MANAGEMENT PLAN

The data management plan will include criteria for the handling and administration of scientific data following the FAIR principles (Findable, Accessible, Interoperable, and Reusable).

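### The planned regressions predict post-treatment and 6-month levels of memory and questionnaire outcomes without each outcome's own pre-intervention score, so a predictor of level cannot be read as a predictor of change

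*Protocol*

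**What the plan says.** The last paragraph of METHODS, 5. Statistical analyses plans that "multiple regression analyses will be performed to predict post-treatment and 6-month follow-up measures (neurocognitive and biopsychological), coding some measures from Study 1 as predictors". It continues with examples: "coding some measures from Study 1 as predictors, such as: processing speed levels, sustained visual attention, verbal fluency, and resistance to visual interference". The targets are the measures themselves, not change from the start of treatment. No further covariate is named for these models.

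The pre-intervention values will be available. METHODS, 3. Outcome variables places the performance tests and the questionnaires both before and after the intervention; for the questionnaires it reads "Secondary variables in pre-/post-intervention phases are questionnaires measuring". METHODS, 4. Procedure adds that the post-intervention assessment repeats the pre-intervention one.

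At six months only questionnaires are listed: "at the 6-month follow-up after the end of both interventions, the BRIEF-2, BASC-3, BPI, AIQ, and PROMIS questionnaires will be included".

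Study 1 scores should exist for every child, because "These 40 patients will be recruited from the sample participating in Study 1".

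**The concern.** Scores of the same child before and after treatment are usually correlated. Suppose a cognitive score is related to, say, BRIEF-2 before treatment. It will then be related to BRIEF-2 afterwards, whether or not it has anything to do with how much the child changes. A regression of the final level on cognitive scores alone cannot separate the two.

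The protocol gives its own reason to expect such a starting correlation. The Background describes deficits in executive functions and somatic symptoms such as chronic pain as varying together. Resistance to interference is a named predictor, and executive function (BRIEF-2) and pain (BPI) are outcomes.

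At stake is the interpretation of a secondary analysis. A cross-sectional correlation that existed before treatment could be taken for information on which children improve.

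**Working it through.** The protocol gives no sample size, alpha or expected correlation for these regressions, so there is no figure of its own to reproduce. The check asks which outcomes are exposed and how large the effect could be.

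**Step 1. Which outcomes have an earlier score of their own among the named predictors?**

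| Outcome | Earlier own-construct score named? | Measured at 6 months? |
|---|---|---|
| SDMT, CPT-3, VFT, STROOP | Yes, from Study 1 | No |
| ECM (memory) | No | No |
| BRIEF-2, BASC-3, BPI, PROMIS, AIQ | No | Yes |
| CAMM | No | No |

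Every outcome listed at 6 months falls in the exposed group.

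**Step 2. Mechanism, one predictor.** Let X be a Study 1 score, Y0 the outcome before treatment and Y1 the outcome after it, all standardised. Let r = corr(X, Y0) and ρ = corr(Y0, Y1), and let X act on Y1 only through Y0. Then:

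- slope of Y1 on X alone = r × ρ
- slope of Y1 on X with Y0 in the model = 0

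For assumed r of 0.3 to 0.5 and ρ of 0.5 to 0.8, the unadjusted slope runs from 0.3 × 0.5 = 0.15 to 0.5 × 0.8 = 0.40. In simulation (4000 runs, two-sided 0.05), X alone is significant in 16% to 75% of runs with 40 patients and in 9% to 43% with 20. With Y0 in the model it is about 5% at both sizes.

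**Step 3. Four predictors, as in the protocol's examples.** Assumed: n = 40 (both waves pooled), predictors intercorrelated 0.4, each correlated r with Y0, ρ = 0.7, no effect on change. The population R² of Y1 on the four predictors is ρ² × 4r² / (1 + 3 × 0.4) = 0.49 × 4r² / 2.2. Rejection rates are from 2000 runs per setting.

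| r | Population R² without Y0 | Model F-test significant, no Y0 | Joint test of the four, Y0 included |
|---|---|---|---|
| 0.2 | 0.49 × 0.16 / 2.2 = 0.036 | 13% | 5.5% |
| 0.3 | 0.49 × 0.36 / 2.2 = 0.080 | 25% | 5.3% |
| 0.4 | 0.49 × 0.64 / 2.2 = 0.143 | 46% | 5.2% |
| 0.5 | 0.49 × 1.00 / 2.2 = 0.223 | 69% | 5.0% |

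Repeat simulations differ from the F-test column by at most about two percentage points, so the range is about 12% to 70%.

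**Step 4. Why a joint test.** Under the assumptions of Step 2 with four predictors, n = 40 and Y0 included, at least one of the four individual t-tests is significant in 17% to 18% of runs. Adding Y0 removes the stand-in effect but not the multiplicity of four separate tests.

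**Step 5. The four overlapping tests.** Suppose the Study 1 score, the pre-intervention score and the post score each measure one stable trait with reliability 0.8, and another predictor correlates 0.5 with that trait. At n = 40 that predictor is significant in 84% of runs with no earlier score in the model, 16% with the Study 1 score and 17% with the pre-intervention score. The Study 1 score does about as much as the pre-intervention score would. Neither reaches 5%, because an imperfectly reliable baseline leaves some starting-level difference behind.

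**The case against.** The strongest reply is that the protocol has excluded nothing. The predictor list is illustrative, full covariate lists are commonly left to the SAP, and no SAP is at hand. Part of this stands: silence is not a stated exclusion, and a Study 1 version of a questionnaire could still enter the model. But the list is open only within measures from Study 1, and the trial's own pre-intervention assessment lies outside that class. The same section fixes the ANCOVA covariate and the individual post hoc tests, so it does settle analysis detail where it chooses to.

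A second reply is that the protocol claims to predict levels, not change or benefit. In the simulations the predictors really are associated with the final level, so a significant F-test is a correct finding about level. This stands. The 12% to 70% is not a false-positive rate for the question as written; it becomes one only if the result is read as prediction of change.

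Three stronger readings are tempting, and the documents do not support them:

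- A reader might infer that all the regressions lack an earlier score of the outcome. For SDMT, CPT-3, VFT and STROOP, a Study 1 score on the same construct is a named predictor.
- A reader might infer that leaving out sequence and wave causes the same problem. METHODS, 4. Procedure allocates both at random. Omitting a randomised factor does not on average turn a baseline score into a spurious predictor; it mainly costs precision.
- A reader might infer that the results are meant to select patients for the intervention. Neither the hypotheses nor the objectives mention predictors or selection.

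**Conclusion.** The point holds in limited form. For ECM, BRIEF-2, BASC-3, BPI, PROMIS, AIQ and CAMM, and so for every outcome listed at 6 months, the stated regressions can show a cognitive score as a predictor when it only reflects where the child started. Such a result describes level and cannot be read as identifying who changes.

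The size is illustrative: about 12% to 70% significant F-tests without the pre-intervention score, against about 5% for the joint test with it. The figures rest wholly on assumed values: 40 patients in the model, predictors intercorrelated 0.4, pre-to-post correlation 0.7, predictor-baseline correlations 0.2 to 0.5, and predictors acting only through the observed pre-intervention score. With a noisy baseline, adjustment would remove most but not all of the effect. This is a secondary analysis, and the comparison with the waiting list does not depend on it.

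**What to change.** In the last paragraph of METHODS, 5. Statistical analyses:

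1. Enter each outcome's own pre-intervention score as a fixed term in its regression, for both the post-treatment and the 6-month targets.
2. Report the added R² and the joint test of the cognitive predictors over that base model, rather than the overall F-test or separate t-tests alone.
3. Describe the result as prognostic among treated patients.
4. Optionally add sequence and wave for precision.

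The cost is wording and a few degrees of freedom. With four predictors and an intercept, 40 patients leave 40 − 5 = 35 residual degrees of freedom. The pre-intervention score brings this to 34, and sequence and wave (one each) to 32. No new data are needed. For the four overlapping tests, the pre-intervention score will be closely related to the Study 1 score of the same construct, so the plan should say whether both stay in the model.

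The same edit can clear a small mismatch. The sentence can be read as planning 6-month neurocognitive outcomes, whereas METHODS, 3. Outcome variables lists only questionnaires at that visit.

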4. Procedure: Participants will be randomized into two subgroups, which will be equally randomized into one of the following two intervention implementation sequences, according to an intragroup Latin square equal weighting technique (AB/BA design). (Fontes-de-Gracia et al., 2020): 1st sequence) Cognitive training (weeks 1-12) + Mindfulness-based emotional regulation (weeks 13-24); 2nd sequence) Mindfulness-based emotional regulation (weeks 1-12) + Cognitive training (weeks 13-24). This equal weighting technique will allow for systematic control of progressive error (order or period), without the need for a washout period between the two interventions, due to a potential residual or carry-over effect, as the treatments do not interfere with each other and are of a different nature (neurocognitive intervention versus emotional intervention).

Each intervention will last 12 weekly sessions, with a total sequence of 24 weeks for both treatments. The group of participants on the waiting list (control group) will remain there until after the 24 sessions, at which point they will begin the same process described above for randomization into subgroups and sequences for implementation of the interventions. Each treatment sequence will have a total of 10 participants assigned to it, in two age-differentiated groups (8-12 versus 13-18 years old), with 5 participants per group. Given this small sample size per group, in order to facilitate smooth interaction among participants, one of the pre-intervention scores (Emotional Regulation Index, BRIEF-2) will be used as a blocking variable, in addition to age, artificially dichotomized according to a cutoff point (resulting in low and high values on that index), thus maximizing the control of extraneous intergroup variables. Consequently, four subgroups of patients will be created by combining the levels of two blocking variables: age (8-12 versus 13-18 years) and Emotional Regulation Index score (low versus high values).

Subsequently, after assigning an anonymized code to each patient, using web-based randomization software, each treatment administration sequence (AB/BA) will be randomly assigned to each of the four patient subgroups.

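### The contingency plan lets patients be added after losses without limiting this to losses before randomisation, and the mixed ANCOVA drops incomplete patients, so the randomised comparison is not secured

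*Protocol*

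**What the plan says.** The Protocol states only one measure for lost patients: "given that participant loss is expected in any clinical trial, additional participants from the previous study will be recruited in such a scenario". It stands in Methods 6 (Limitations, biases, and contingency plan), which does not say until when an additional patient may enter, or how that patient is allocated.

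The design around it is in Methods 2, 4 and 5:

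- **Size and source.** Methods 2 plans "A total of 40 patients (20 patients initially in the clinical trial phase and 20 on the waiting list", and adds: "These 40 patients will be recruited from the sample participating in Study 1 using a strategic/intentional non-random sampling technique".
- **Allocation.** Methods 4 says "Participants will be randomized into two subgroups, which will be equally randomized into one of the following two intervention implementation sequences". It then says "Each treatment sequence will have a total of 10 participants assigned to it, in two age-differentiated groups", with five patients per group. Four subgroups are formed from age band and Emotional Regulation Index, and "each treatment administration sequence (AB/BA) will be randomly assigned to each of the four patient subgroups".
- **Analysis.** Methods 5 begins: "First, mixed 2x3 ANCOVAs will be used", with three occasions (before, after, six months). Latent growth curve models are to be developed as well. No estimator is named for them.

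The Protocol names no analysis set. A statistical analysis plan, not shown, may do so.

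**The concern.** Who may enter the trial, when, and by what allocation is a matter of conduct, and the Protocol settles part of it: losses are met by recruiting more patients. The design leaves little room for such a patient to be randomised. Once each subgroup has its sequence, the age band and index category of a late entrant determine the sequence. A patient recruited because a treated group has lost a member would naturally join that group.

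The standard mixed ANCOVA needs every occasion, so the patient who left would also drop out of the main analysis. Together, these two steps would replace a comparison of patients as randomised with one of patients who stayed, supplemented by patients placed in a known arm. With 20 per arm, each substituted patient is 1/20 = 5% of the arm.

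**Working it through.** **1. The plan's own count.** 2 sequences x 2 age groups x 5 patients = 20 in the intervention arm. Adding 20 on the waiting list gives 40, which agrees with Methods 2. The Protocol gives no dropout rate, alpha, power or effect size, so every input below is an assumption shown as a range.

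**2. Is there a random draw for a late entrant?** Methods 4 describes two draws: patients into two subgroups, and sequences onto the four blocked subgroups. Both are described for the initial cohort. After they are made, no further draw is described for a single new patient. Slot-filling is therefore likely but is not written down.

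**3. Bias if losses are left out, simple form.** Let d be the share lost in one arm and g the amount, in SD, by which those lost would have scored worse than those who stay. The completer mean exceeds the mean of all patients by d x g:

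- 0.1 x 0.3 = 0.03 SD
- 0.2 x 0.5 = 0.10 SD
- 0.3 x 0.8 = 0.24 SD

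**4. The same with a dropout model.** Assume losses in the intervention arm only, a true effect of zero, and correlation rho between outcome and the tendency to stay. Then bias = rho x phi(z_d)/(1 - d), where phi is the normal density and z_d the d-quantile. A simulation checked this: 4,000 runs per setting, lost patients replaced in the vacated slot until the arm had 20 completers, compared with 20 controls by a two-sided t-test at 0.05.

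| d | phi(z_d)/(1 - d) | Bias at rho = 0.3: formula / simulated (SD) | Bias at rho = 0.5: formula / simulated (SD) | Rejection rate at rho = 0.5 |
|---|---|---|---|---|
| 0.1 | 0.195 | 0.058 / 0.065 | 0.097 / 0.100 | 6.1% |
| 0.2 | 0.350 | 0.105 / 0.106 | 0.175 / 0.177 | 8.5% |
| 0.3 | 0.497 | 0.149 / 0.145 | 0.248 / 0.247 | 12.0% |

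At rho = 0 the formula gives zero at every d, and the simulated bias was within 0.002 SD of zero.

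**5. The same runs with every enrolled patient kept and measured.** Bias was at most 0.010 SD and the rejection rate 4.3% to 5.4%. This assumes that outcomes are obtained for those who left.

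**6. What the figures measure.** Steps 3 and 4 give the bias from analysing completers only. It is the same size whether or not the vacant places are refilled. Placing a non-randomised patient in a known arm is a separate selection problem, and the documents give nothing from which to size it.

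**The case against.** The strongest reply is that the Protocol states neither step. It does not say that additional patients take a vacated place, and the web-based randomisation in Methods 4 exempts no one. The project stages put the experimental group's pre-intervention assessment in November-December 2025 and its sessions from March 2026. Losses before allocation could thus be replaced quite properly. Nor does any text exclude lost patients. The analysis set may be in the statistical analysis plan, and latent growth models can use incomplete records if fitted by full-information likelihood. All of this stands, and it is why the point is conditional.

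Four stronger readings are tempting but not supported:

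- **That replacement in itself breaks the randomisation or makes this an analysis of completers.** A later entrant who is newly randomised does no such harm, and the omission of incomplete patients comes from the ANCOVA.
- **That the bias favours treatment.** Treated patients do carry one 60-minute call plus 4 x 15 minutes a week, 120 minutes in all, for 24 weeks. However, the rule on adherence below 50% in Methods 4 is conditional, covers the cognitive platform only, and concerns use of the platform, not loss to assessment. Waiting-list patients may leave too, which would reverse the sign.
- **That attrition would be hidden behind an n of 40.** Methods 1 commits to CONSORT standards, whose flow diagram should show it.
- **That purposive sampling biases the arms.** Applied before randomisation, it limits generalisability only. It matters here only if a chosen patient enters an arm that is already known.

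The reply does not answer the missing limit. Methods 6 permits additions after allocation, Methods 4 describes no draw for them, and the first-named model discards partial records.

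**Conclusion.** The concern holds in conditional form. If additions after allocation fill known places, if lost patients leave the analysis, and if dropout is related to outcome, the comparison is no longer protected by randomisation. Under the assumed inputs (10-30% lost from one arm; an outcome gap of 0.3-0.8 SD, or rho of 0.3-0.5) the completer-only bias is roughly 0.03-0.25 SD. At rho = 0.5 the false-positive rate is about 6-12% in place of 5%. With uninformative dropout the bias is zero. The documents establish neither the dropout rate nor the direction. The case for changing the text is that a better rule is available at little cost. It does not rest on any demonstrated bias.

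**What to change.** Change Methods 6 and Methods 5 as follows:

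- Allow replacement only for patients lost before randomisation.
- Keep every randomised patient in the analysis in the assigned arm and sequence.
- Invite patients who stop sessions to the planned post-intervention in-person tests as well as the electronic questionnaires. The primary variables are performance tests taken at the hospital, so questionnaires alone would leave them missing.
- Use a likelihood-based mixed model for repeated measures, which uses all observed visits, in place of the mixed ANCOVA. The performance tests are planned only before and after treatment. A patient without the second test contributes only a baseline, and the model cannot make up for a missed invitation.
- Any later entrant is either newly randomised by the same web-based procedure and shown separately in the CONSORT flow diagram, or attends sessions but is left out of the randomised comparison.

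The cost is a few sentences of protocol text, some effort to bring back patients who have stopped, and fewer than 40 completers if losses occur: for example 20 x 0.7 = 14 of 20 in an arm at an assumed 30% loss. If 40 completers are wanted, more patients can be randomised at the start. 40/(1 - d), rounded up, gives 45, 50 or 58 for assumed losses of 10%, 20% or 30%, and the group sizes would then need to be revised.
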